Project title:

Pilot study: Influence of ischemic preconditioning on the orthostatic competence of the microcirculation in the lower extremity

Date: 20.07.2023

1) Studyprotocol

Procedures for informing and obtaining consent:

The recruited subjects will be informed about the nature, importance, risks and scope of the intended scientific investigation in a personal interview with one of the investigators and will receive patient information. After sufficient time for reflection, the consent will be confirmed in writing on the form prepared for this purpose - declaration of consent.

Measures:

The experimental setup consists of two separate measurements. In the first measurement, the subject is ortho-statically stressed by changing the position (lying to upright) on a tilting table (similar to the established tilting table test). 24 hours after the first measurement, the ischemic preconditioning will be carried out in three cycles with a directly subsequent tilting table test.

1. Tilting table

Time (min)	0-15	15-30	30-45	24 h Break
Position	lying	upright	lying	

Ischemic preconditioning and 2. Tilting table

Time (min)	0-10	10-20	20-30	30-40	40-50	50-60	60-75	75-90	90-105	30-45
Procedures	Ischemia		Reperfusion	Ischemia		Reperfusion	Ischemia			
Position	lying								upright	lying

The measurements are carried out in a room with a constant temperature of 21° without a window. The test subjects should not do any sport or drink alcohol for 24 hours beforehand and not drink coffee for 6 hours beforehand.

The respective tilting table measurements are carried out in the same way: The subject is laid down on the tilting table (standing board 20.200, RFH-Rehatechnik GmbH, Bayreuth, Germany). The fixation of the 3 mm probe (O2C® Laser Doppler and tissue spectrometry LEA Medizintechnik GmbH, Giessen, Germany) for measuring the microcirculation is stucked of on the antero-lateral thigh (potential donor area of an ALT flap) in a standardized manner with transparent plaster (CURAPOR® cannulas Fixation plaster i.v.). A non-invasive, continuous blood pressure measurement on the left arm and ring finger (Finapres® NOVA, Finapres Medical Systems BV, Enschede, Netherlands) is used for precise circulatory monitoring. The subject is fixed to the tilting table with belts. During the entire measurement, the subject is asked to lie relaxed and not to make any active movements.

After 15 minutes, the tilting table or the subject on the tilting table is tilted fully automatically (electrically) from a horizontal (0°) to an upright (80°) position. The subject remains in this position for 15 minutes. Then the tilting table or subject on the tilting table is tilted fully automatically (electrically) again from the upright (80°) to a horizontal (0°) position or position. The subject remains lying down (starting position) for further 15 minutes. The first measurement is then ended.

The second measurement with previous ischemic preconditioning is carried out under identical conditions. Positioning the patient on the tilting table and attaching the monitor is identical to the first measurement. The empty tourniquet (VBM Tourniquet Touch®, Sulz a.N. Germany) is attached to the right upper arm. The measurement starts from this point in time. After lying flat for 10 minutes, the upper arm tourniquet is inflated to 250mmHg. In all subjects, the ischemia was verified by palpation and Doppler signal of the radial artery. The ischemia phase is carried out for 10 minutes, so the tourniquet is opened, and a 10-minute reperfusion phase is started, followed by a total of 3 cycles. After the 3rd ischemia phase, the tilting table test – as described above – followed with a 15-minute lying interval.

2) Statistical Analysis Plan

Since there will be non-normal distribution and little data, we will use non-parametric tests. The Wilcoxon test compares the values of dependent samples (pre and post). If the p-value (level of significance) is < 0.05 , then it would be significant and there would be differences between the pre and post values. If the p-value (level of significance) > 0.05 , then it would not be significant and there would be no differences between the pre and post values.

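### Subjects are tilted after 15 min supine in session 1 and after about 75 min in session 2, so the preconditioning contrast is mixed with about 60 extra minutes of immobile rest

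*Protocol*

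**What the plan says.** All of this is in the Protocol, 1) Studyprotocol, under Measures.

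- **Order and spacing:** "24 hours after the first measurement, the ischemic preconditioning will be carried out in three cycles with a directly subsequent tilting table test". Every subject has the session without preconditioning first.
- **Session 1:** "After 15 minutes, the tilting table or the subject on the tilting table is tilted fully automatically (electrically) from a horizontal (0°) to an upright" position. It continues with 15 min upright and 15 min lying. No cuff is mentioned.
- **Session 2:** "The empty tourniquet (VBM Tourniquet Touch®, Sulz a.N. Germany) is attached to the right upper arm", and the measurement clock starts at that moment. Then: "After lying flat for 10 minutes, the upper arm tourniquet is inflated to 250mmHg". Ischemia and reperfusion phases last 10 min each, with three cycles in total. After the third ischemia the tilt test "followed with a 15-minute lying interval".
- **Comparability:** "The second measurement with previous ischemic preconditioning is carried out under identical conditions", followed by "Positioning the patient on the tilting table and attaching the monitor is identical to the first measurement".
- **Immobility:** subjects are belted to the table and asked to avoid active movement throughout each measurement.

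The statistical section, 2) Statistical Analysis Plan, names one test: a paired Wilcoxon test of pre against post values at the 0.05 level. It gives no sample size and does not tie pre and post to a session or a tilt phase.

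**The concern.** The title asks how ischemic preconditioning influences the orthostatic response of the leg microcirculation. Session 1 is the only condition without preconditioning, so any answer has to come from comparing session 2 with session 1.

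The two sessions differ in more than preconditioning. Total supine time, time strapped still, probe time on the skin and cuff presence all differ before the tilt. The outcome is a response to a change of posture, and the length of the preceding posture is one of the things that changed. A longer rest could imitate a preconditioning effect or hide one. The claim of identical conditions would lead a reader to think this had been controlled.

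**Working it through.** **Supine time before tilt, from the stated phases**

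| Phase | Session 1 (min) | Session 2 (min) |
|---|---|---|
| Initial rest | – | 10 |
| Ischemia | – | 3 × 10 = 30 |
| Reperfusion between ischemias | – | 2 × 10 = 20 |
| Lying interval before tilt | 15 | 15 |
| **Supine before tilt** | **15** | **10 + 30 + 20 + 15 = 75** |
| Upright, then lying | 15 + 15 | 15 + 15 |
| **Session length** | **45** | **105** |

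The gap is 75 − 15 = 60 min, a ratio of 75/15 = 5. The session 2 total agrees with the protocol's timetable, whose time labels run on through 60–75, 75–90 and 90–105.

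Other readings only widen the gap. A third full reperfusion before the lying interval gives 75 + 10 = 85 min, a gap of 70. Taking the timetable's upright cell literally, under 90–105, gives 90 min, a gap of 75. That table did not survive text extraction cleanly, so I do not rely on its cells. Sixty minutes is the smallest gap the document supports.

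**Why analysis cannot separate the effects**

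For subject *i*, write the between-session difference as

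D_i = τ + ρ + ω + e_i,

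where τ is the preconditioning effect, ρ the effect of the extra supine time (with cuff presence), ω the effect of coming second, 24 h after a first tilt, and e_i is error. Every subject receives all three together, so only τ + ρ + ω can be estimated. If D_i is built from lying-to-upright changes, additive baseline drift such as probe settling cancels. An effect of longer rest on the tilt response itself stays in ρ.

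**What a rest effect could do (illustration only)**

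The document gives neither n nor ρ. I assume n = 10, 20 or 30, normally distributed paired differences, ω = 0, and shifts in units of the SD of D_i. The test is the two-sided exact signed-rank test (the protocol does not state sidedness), with attained levels of 0.0488, 0.0484 and 0.0497. Each cell has 200,000 simulated trials, so the Monte Carlo standard error is at most √(0.25/200,000) ≈ 0.001.

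| Net shift (τ + ρ) | n = 10 | n = 20 | n = 30 |
|---|---|---|---|
| τ = 0, ρ = 0 | 0.049 | 0.048 | 0.049 |
| τ = 0, ρ = 0.1 | 0.058 | 0.069 | 0.081 |
| τ = 0, ρ = 0.25 | 0.106 | 0.177 | 0.254 |
| τ = 0.5, ρ = 0 | 0.283 | 0.541 | 0.734 |
| τ = 0.5, ρ = −0.1 (net 0.4) | 0.200 | 0.378 | 0.541 |
| τ = 0.5, ρ = −0.25 (net 0.25) | 0.106 | 0.176 | 0.254 |

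The second and third rows show false-positive rates when preconditioning does nothing. The last two show power lost when rest works against a real effect.

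**The case against.** The strongest reply has five parts.

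- **The wording.** The sentence names preconditioning as the exception, and the next sentence limits the identity to positioning and monitor attachment. The extra time is openly shown. This stands in part: the phrase is fair for the room, set-up and tilt sequence, and the finding is about the design more than a false statement.
- **The extra time is the intervention.** Of the 60 min, 50 (30 + 20) are the cycles and only 10 are plain rest. This is true, but the subject lies still throughout, and session 1 has no counterpart. Calling the time part of the package means the study estimates the package, not preconditioning.
- **The last 15 min are matched.** They are, and change scores would remove additive drift. Total supine time and its effect on the tilt response remain unmatched.
- **The percentages are generic.** This is accepted. They would apply to a shift from any cause, and the protocol itself expects non-normal data. Only the 15 and 75 min are this trial's own figures.
- **This is a pilot, and the fix leaves session order confounded.** Both are true. A pilot whose signal cannot be attributed is still a weak basis for a later trial, and time-matching removes one of two confounders at low cost.

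The undefined pre and post values could mean a within-session test. A statement about preconditioning would still need the between-session comparison.

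**Conclusion.** The concern holds and should be fixed. Supine time before tilt is 15 min in session 1 and about 75 min in session 2, and no time-matched rest or cuff is described for session 1. Preconditioning and the extra 60 min coincide in every subject, so no analysis can separate them. This rests on the phase durations in the text and on reading the question as a between-session comparison, which the title implies.

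Whether the bias is large, small or absent cannot be determined from the document. The illustrative rejection rates depend wholly on assumed sample sizes and effects. The fixed order is a further confounder, separate from the difference in rest.

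**What to change.** **Preferred:** run session 1 on session 2's clock. Attach the same cuff to the right upper arm, leave it uninflated, and keep the subject supine with the probe in place for as long as session 2 takes before its lying interval (60 min by the text: 10 + 30 + 20). Then do the same 15/15/15 tilt test. This lengthens session 1 from 45 to 105 min, about 60 min more of subject, staff and room time per subject. It needs one protocol amendment and no new equipment.

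**Fallback, including if measurements have already been made:** limit the claim of identical conditions to room, positioning, monitoring and tilt sequence. Compare the lying-to-upright change between sessions, and restrict the conclusion to the combined effect of preconditioning plus prolonged supine rest. This costs only wording and a narrower conclusion.

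**In either case,** state that the fixed order, with control first and preconditioning 24 h later, is a separate confounder that time-matching does not remove.

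### Does the protocol leave open whether the day-2 upright phase runs at 75-90 or at 90-105 minutes?

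*Protocol*

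**What the plan says.** Protocol section 1 (Measures) announces the second session as preconditioning in "three cycles with a directly subsequent tilting table test". It says that both tilt measurements are done alike and describes the test once, for day 1: 15 minutes lying, 15 minutes upright, 15 minutes lying. The first timetable shows the same limits (0-15, 15-30, 30-45).

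On day 2 the prose starts with rest: "After lying flat for 10 minutes, the upper arm tourniquet is inflated to 250mmHg". Ischemia then lasts 10 minutes, after which "a 10-minute reperfusion phase is started, followed by a total of 3 cycles". The tilt test is attached to this as follows: "After the 3rd ischemia phase, the tilting table test – as described above – followed with a 15-minute lying interval".

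The second timetable has six headers of 10 minutes, up to minute 60, and ends with "75-90 90-105 30-45" after the header 60-75. Section 2 (Statistical Analysis Plan) names the paired comparison: "The Wilcoxon test compares the values of dependent samples (pre and post"). It gives no minute limits.

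**The concern.** The linking sentence is clumsy. It can be heard as the full tilt test, or as a lying interval followed by the full tilt test. On the second hearing the subject lies for 30 minutes before being tilted.

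The timetable appears to back that hearing. Ten headers need ten phases, and the prose yields nine. As printed, the upright entry stands under 90-105 and the last lying entry under the tenth header. Three cycles of ischemia plus reperfusion also suggest a third reperfusion that has no slot of its own.

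If the schedule were truly open, the matter would not be trivial. The delay from cuff release to tilting is part of the condition being compared. The windows 75-90 and 90-105 share no minute, so a recording cut by the wrong schedule would label a lying phase as upright or the reverse.

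**Working it through.** **Check on day 1.** 15 + 15 + 15 = 45 minutes, with limits 0-15, 15-30 and 30-45. This reproduces the first timetable.

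**Day 2 from the prose.** The inputs are 10 minutes lying, three ischemias of 10 minutes, two reperfusions of 10 minutes between them, and the tilt test of three 15-minute phases.

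- End of the third ischemia: 10 + 3×10 + 2×10 = 60 minutes.
- Tilt test: lying 60-75, upright 75-90, lying 90-105.
- Total: 60 + 3×15 = 105 minutes, nine phases. Delay from release to tilt: 75 − 60 = 15 minutes.

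**The supposed alternative.** A separate lying interval before the full test gives 60 + 4×15 = 120 minutes, ten phases, upright 90-105 and a delay of 90 − 60 = 30 minutes.

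**Prose against timetable.** The third column shows the entries as they stand in the extracted table (procedures, and positions in the last two rows).

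| Header | Phase from the prose | Entry as extracted |
|---|---|---|
| 0-10 | lying | ischemia |
| 10-20 | ischemia 1 | blank |
| 20-30 | reperfusion 1 | reperfusion |
| 30-40 | ischemia 2 | ischemia |
| 40-50 | reperfusion 2 | blank |
| 50-60 | ischemia 3 | reperfusion |
| 60-75 | lying | ischemia |
| 75-90 | upright | blank |
| 90-105 | lying | upright |
| 30-45 | none | lying |

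Four things follow.

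1. The first nine headers are the nine phases of the prose, limit for limit: 6×10 + 3×15 = 105 minutes. The 120 minutes appear only if 30-45 is counted as 15 further minutes after minute 105. No header reads 105-120.
2. The cells are displaced. Ischemia stands in the first 10 minutes, where the prose has rest before inflation, and the third ischemia stands in a 15-minute column although it lasts 10. From the second reperfusion onward each procedure entry sits one column to the right of its place in the prose.
3. Undoing that one-column shift in the position row moves upright from 90-105 to 75-90 and the last lying phase from the tenth header to 90-105. That is the prose schedule.
4. Even as printed, only one column (75-90) lies between the third ischemia and upright. If release is at 75, as that column implies, the delay is 90 − 75 = 15 minutes. A delay of 30 minutes needs the release time from the prose and the upright time from the displaced row.

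**Third reperfusion.** A separate 10-minute slot would give lying 70-85, upright 85-100 and a total of 115 minutes, with a delay of 25 minutes. These limits fit none of the headers after minute 60. The order of the procedures row is ischemia, reperfusion, ischemia, reperfusion, ischemia. That agrees with the prose, which goes from the third ischemia to the tilt test.

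**The case for a change.** The best argument for the concern avoids cell positions altogether: ten headers against nine phases is a mismatch however the cells are aligned, and a header of 30-45 after 90-105 cannot be right as printed. The linking sentence is also loosely built, and a reader who trusts the position row as it stands would tilt at minute 90.

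The header is indeed out of sequence, and that much stands. It does not establish a second schedule. The same label closes the day-1 table, so a leftover from copying, or a fault in reading the table from the PDF, explains it without any extra phase. The ten-phase reading needs the opposite: a label that is wrong and should read 105-120, together with a lying interval that no sentence states. It also sits badly with a tilt test said to follow directly and to be the one already described.

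The remark about cycles stands as loose wording. With two reperfusions between three ischemias, the phase after the last release is simply the lying phase of the tilt test.

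The wish to fix the pre interval in section 2 by minute limits, or to report a resting change descriptively, does not follow from the timetable. Analysis windows may be set in a fuller analysis plan, and the descriptive summary would be a preference.

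**Conclusion.** There is no contradiction of substance. The prose gives one day-2 schedule of 105 minutes, with upright at 75-90 and tilting 15 minutes after the last release, and nine of the ten headers reproduce it exactly. The contrasts of 15 against 30 minutes and 105 against 120 minutes depend on a single stray header and on displaced cells.

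The conclusion assumes that the lying interval in the linking sentence is the opening phase of the tilt test, which is what the reference back to the day-1 description and the direct succession both indicate. It also assumes that the cell displacement is a layout or extraction fault. It is a statement about what the document says, not a judgement on whether that interval is clinically suitable. A team following the text would run, and cut the recordings by, one schedule. The out-of-sequence label and the wording about cycles are clerical and affect neither the paired comparison nor any figure in section 2.

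### The pilot's stated inference is a yes/no verdict from a Wilcoxon p-value; it should be a signed estimate with an exact interval and the within-subject spread

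*Protocol*

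**What the plan says.** The protocol title describes the study as "Pilot study: Influence of ischemic preconditioning on the orthostatic competence of the microcirculation in the lower extremity". Under Measures, the design is within-subject: "The experimental setup consists of two separate measurements", one tilt-table test without preconditioning and one after it, 24 hours apart.

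Section 2, Statistical Analysis Plan, is four sentences long. The first gives the reason for the method: "Since there will be non-normal distribution and little data, we will use non-parametric tests". The second names the Wilcoxon test for dependent samples. The last two state the whole inference rule:

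- "If the p-value (level of significance) is < 0.05", "then it would be significant and there would be differences between the pre and post values".
- Above 0.05, "then it would not be significant and there would be no differences between the pre and post values".

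The section mentions no estimate of the change, interval, measure of spread or direction. It does not say whether the p-value is exact or approximate, or one- or two-sided. The document gives no number of subjects.

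**The concern.** The title asks about influence, which has a direction and a size. The rule in section 2 answers only whether the two sets of values differ. If preconditioning significantly impaired the microcirculatory response, the stated conclusion would be the same as if it had improved it.

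A pilot is also where the next study gets its planning inputs: the likely direction, a rough size with its uncertainty, and the variability of the within-subject change. None of these is an output of the rule. Because the plan itself expects few data, a bare verdict also hides how imprecisely the effect is known, whichever side of 0.05 the p-value falls.

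**Working it through.** The plan contains no sample size, power or effect figure, so there is nothing of its own to reproduce. The check is what the rule returns for data sets that differ in what matters.

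**Inputs.** From section 2: paired Wilcoxon (signed-rank) test and threshold 0.05. Assumed: 8 non-zero pairs without ties, because no number is given, and a two-sided test, because the verdict is about differences in either direction.

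**Step 1: the verdict.** When all n differences have the same sign, the smaller rank sum is W = 0 and the exact two-sided p-value is 2/2^n. For n = 8 this is 2/256 = 0.0078.

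**Step 2: what an estimate adds.** The Hodges-Lehmann estimate is the median of all pairwise averages of the differences, each difference also being averaged with itself. For n = 8 there are 8 × 9/2 = 36. Under the null hypothesis, P(W ≤ 3) = 5/256, so the exact interval runs from the 4th smallest to the 4th largest average, with coverage 1 - 10/256 = 96.1%. For differences 1 to 8 the smallest averages are 1, 1.5, 2 and 2, so the lower limit is 2. By symmetry the upper limit is 7 and the estimate 4.5. The other rows follow by change of sign or scale.

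| Paired differences | Exact p | Planned conclusion | Estimate (exact interval) |
|---|---|---|---|
| +1 to +8 | 0.0078 | differences | 4.5 (2 to 7) |
| -1 to -8 | 0.0078 | differences | -4.5 (-7 to -2) |
| +0.01 to +0.08 | 0.0078 | differences | 0.045 (0.02 to 0.07) |
| +10 to +80 | 0.0078 | differences | 45 (20 to 70) |

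The last two rows differ 1000-fold (45/0.045). The verdict column cannot tell the four rows apart; the estimate column can.

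**Step 3: does the unspecified p-value method matter?** The exact null distribution was enumerated for n = 4 to 20, 25 and 30. It was compared with the large-sample p-value from z = (n(n+1)/4 - W)/√(n(n+1)(2n+1)/24), without continuity correction. For n = 8 and W = 4, z = (18 - 4)/√51 = 1.96, so p = 0.0499, against an exact p of 14/256 = 0.0547. The two verdicts differ at one rank sum only, and only for these n:

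| n | True error rate of the uncorrected version |
|---|---|
| 5 and 6 | 6.25% |
| 8 | 5.47% |
| 12 | 5.22% |
| 16 | 5.07% |
| 17 | 5.05% |

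With continuity correction, the true error rate is never above 5% at any n checked.

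**The case against.** **A fuller plan may exist.** Estimates, intervals and computational detail are commonly left to a separate analysis plan, and nothing in section 2 forbids reporting them. This stands as a caution: one cannot say that the sponsor will report no estimates. But the section carries the title of an analysis plan and states a complete rule for drawing conclusions. A fuller plan would have to replace that rule, not merely add to it.

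**The sentence about p < 0.05 is not false.** Concluding that there is a difference is the ordinary reading of a significant two-sided test, and the direction can be read from the data because the signed-rank statistic carries a sign. This stands too. The fault is that the stated conclusion stops there.

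**A reader might infer that the false-positive rate materially exceeds 5%.** The document does not support this. It does not choose the large-sample p-value, and even the uncorrected version is above 5% only at the few n in step 3, by at most 1.25 percentage points. Naming the exact distribution is tidy but minor.

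**A reader might infer that an estimate with an interval cures the exaggeration of significant results in small studies.** It does not. Assuming normal differences and a true effect of 0.5 SD, the Hodges-Lehmann estimate among results with p < 0.05 averages 1.79, 1.65 and 1.31 times the true value at n = 8, 10 and 20. The interval shows imprecision; it does not undo selection on significance.

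**Conclusion.** The point holds as one about the form of the inference. The rule in section 2, followed as written, returns the same conclusion for benefit and harm and for effects 1000-fold apart, and yields no size, interval or within-subject spread. That first part holds for any number of pairs at which the test can reach p < 0.05, because the signed-rank p-value does not change when all differences are multiplied by a constant or reversed in sign; the 8 pairs are only an illustration.

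The data collected are not invalidated, and the paired non-parametric test is not itself wrong. What is at risk is the use of the pilot: its conclusion would not describe the influence named in the title, nor supply planning inputs. This rests on section 2 being the operative plan.

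**What to change.** In section 2, for each pre/post contrast:

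- Make the main result the Hodges-Lehmann estimate of the paired differences, with its sign, the order of subtraction stated, and its exact 95% confidence interval with attained coverage.
- Report the spread of the within-subject differences (SD or IQR) and how many subjects rose and how many fell.
- Replace both yes/no sentences with a conclusion that gives direction and size with the interval.
- Keep the two-sided Wilcoxon p-value, computed from the exact signed-rank distribution, as supportive. No separate minimum number of pairs is needed: with five pairs the smallest exact p-value is 2/2^5 = 0.0625, so the test cannot reach 0.05.

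**Cost.** A few sentences; no extra subjects, measurements or visits. The interval will be wide and a significant result will look less decisive. The spread will be imprecise too: with an assumed 10 pairs and normal differences, the 95% limits for the SD, √(9/χ²), are 0.69 and 1.83 times its estimate. Normality is an assumption here and runs against the plan's own expectation. The estimate and its exact interval assume roughly symmetric differences, as does reading the signed-rank test as a test of the typical change.

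### The plan reads p > 0.05 as showing no difference; a non-significant Wilcoxon test does not show that, least of all in a small pilot

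*Protocol*

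**What the plan says.** Section 2 of the protocol (Statistical Analysis Plan) chooses the method on these grounds: "Since there will be non-normal distribution and little data, we will use non-parametric tests". It names one test, the Wilcoxon test for dependent samples, and then fixes how its result is to be read, in two branches:

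- Significant: "If the p-value (level of significance) is < 0.05 , then it would be significant and there would be differences between the pre and post values".
- Not significant (p above 0.05): "then it would not be significant and there would be no differences between the pre and post values".

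There is no third, inconclusive outcome. The protocol states no number of subjects, effect size, power or equivalence margin. The title calls the work a pilot study, and the section on measures describes two tilting-table measurements per subject, the second with preconditioning.

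**The concern.** The second branch treats failure to reject the null hypothesis as proof of it. A signed-rank test with p above 0.05 says that the data do not rule out a zero shift. It does not say that they rule out a shift worth knowing about. To conclude that there is no relevant difference, one needs an interval judged against a margin set in advance.

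If a comparison comes out non-significant and the rule is followed, the report will say that the values with and without preconditioning do not differ, although the data may be compatible with a sizeable effect. For a pilot, such a reading could wrongly discourage further work. If p is below 0.05, the sentence has no effect.

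**Working it through.** **The logical point.** This needs no arithmetic. The plan's inference runs from p > 0.05 to no differences. The valid inference stops at a difference not having been demonstrated. The gap exists at every sample size.

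**Inputs for an illustration.** From section 2: paired Wilcoxon test, threshold 0.05, few data. Two-sided testing is assumed, because the rule speaks only of differences. The number of pairs n, the true shift and the shape of the paired differences are not given, so all three are assumed and varied. The plan has no figure of its own to reproduce.

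**Step 1: the smallest attainable p.** For the exact signed-rank test without ties or zeros, the smallest two-sided p is 2/2^n.

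- n = 5: 2/32 = 0.0625
- n = 6: 2/64 = 0.03125

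With 5 or fewer pairs the exact test can never fall below 0.05, so the rule would always report no difference, whatever the truth.

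**Step 2: how often a real shift is declared absent.** The null distribution of the signed-rank statistic was computed exactly. The test rejects when min(W+, W−) is at most 8, 25, 52 and 137 for n = 10, 15, 20 and 30. Paired differences were scaled to SD 1, shifted by the assumed effect and simulated 100,000 times per cell. The share with p > 0.05 equals 1 − power. For a true shift of 0.5 SD:

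| Distribution of differences | n = 10 | n = 15 | n = 20 | n = 30 |
|---|---|---|---|---|
| Normal | 71.8% | 58.1% | 45.7% | 26.6% |
| Laplace | 62.9% | 46.7% | 33.3% | 15.7% |
| t, 3 df | 54.0% | 35.8% | 22.0% | 7.5% |

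Larger shifts:

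| True shift and n | Normal | Laplace | t, 3 df |
|---|---|---|---|
| 0.8 SD, n = 10 | 40.5% | 34.2% | 24.6% |
| 0.8 SD, n = 20 | 9.0% | 6.0% | 2.3% |
| 1.0 SD, n = 15 | 6.2% | 5.5% | 2.8% |

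Separate simulations of the normal and t cells at 0.5 SD (40,000 runs each) agreed to within half a percentage point.

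**Step 3: what a non-significant result leaves open.** An approximate 95% interval for the mean paired difference has half-width t(0.975, n − 1)/√n, in SDs of the differences:

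- n = 6: 1.05
- n = 10: 0.72
- n = 20: 0.47
- n = 30: 0.37

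At n = 10, an observed difference near zero would therefore still be compatible with a shift of about 0.7 SD in either direction.

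To look at this directly, non-significant results were taken from 20,000 simulations per cell at a true shift of 0.5 SD. The share whose 95% interval (from the inverted signed-rank test) still contained 0.5 SD was:

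| Distribution | n = 10 | n = 20 | n = 30 |
|---|---|---|---|
| Normal | 96.6% | 94.3% | 90.6% |
| Laplace | 96.3% | 92.6% | 86.1% |

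In these cells, most results that the plan would label as no difference are compatible with the true effect.

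**The case against.** The strongest reply is that this is loose English for no significant differences and changes no test, threshold or p-value. The effect on the trial is indeed confined to interpretation. But the sentence joins two statements, that the result is not significant and that there are no differences, and the second adds a conclusion to the first. The significant branch takes the same step. Followed as written, the rule puts the stronger claim in the report.

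Three further points have weight:

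- **The miss rates measure power.** Rewording would leave the same share of results non-significant; it changes only what is said about them. That is correct, and the rates should be read as how often the faulty sentence would mislead.
- **The frequency depends on unknown inputs.** For large effects, or near 30 pairs with heavy tails, misreading is uncommon. The only hints in the document are the pilot label and the expectation of few data.
- **The interval result is not general.** For t (3 df), n = 30 and 0.5 SD the share is about 76%. For normal differences at 0.8 SD it is about 80% at n = 20 and 42% at n = 30, although at n = 30 only about 1.5% of results are then non-significant.

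The protocol also contains no progression rule, so harm to later research is a possibility, not a stated consequence. Estimates and intervals may be planned in a separate analysis plan that is not at hand, and their absence here is not counted as an error.

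**Conclusion.** The concern holds: the sentence is wrong as written, and nothing else in the protocol corrects it. That conclusion rests on the stated rule alone and on no assumption about size or effect.

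How often it would mislead is conditional. With moderate effects (0.5 SD of the paired differences) and 10 to 15 pairs, roughly 36% to 72% of studies would declare a real shift absent, depending on the distribution. With a 1.0 SD effect at 15 pairs the figure is about 3% to 6%. The correction should be made, but it is a fault of interpretation and not of design or testing.

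**What to change.** Replace the sentence on non-significant results with: *If p is 0.05 or greater, a difference has not been demonstrated; this is not evidence of no difference.* This alone cures the error. It also covers p exactly equal to 0.05, which falls under neither of the present branches.

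As an optional supplement, report each paired comparison with an estimate and 95% confidence interval, for example the Hodges–Lehmann estimate with the interval from the inverted signed-rank test. That assumes roughly symmetric paired differences. Where this is doubtful, give the median paired difference with a sign-test interval, which is usually wider. If the investigators want to be able to claim that there is no relevant difference, they must set an equivalence margin in advance.

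The cost is one sentence of wording, plus one extra output per test if intervals are added. No new data are needed, and the test and p-value stay the same. The price is a more cautious conclusion when p is not below 0.05.
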